9.2.3 Post-scan Treatment Options

Patients may receive salvage treatment following further consultation with their physician (outside the scope of this study). The salvage treatment prescribed will be recorded. If treatment consists of a surgical resection, the histology obtained will be correlated with rhPSMA-7.3 (18F) PET imaging. Follow-up confirmatory imaging should not delay the patient's treatment.

9.2.4 Clinical Management

The impact of the rhPSMA-7.3 (¹⁸F) PET imaging results on patients' intended clinical management will be assessed by means of both a pre-PSMA PET scan (completed prior to rhPSMA-7.3 (¹⁸F) imaging) and post-PSMA PET scan clinical utility questionnaire, in which the investigator will record any changes to the patients' intended management plan based on the rhPSMA-7.3 (¹⁸F) PET scan.

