10.2 Visit 2 (Day 1; IP Administration)

1. Record any changes in concomitant medication since screening (omit if Visit 1 and Visit 2 are combined; see [Section 10.3](#)).
2. Perform and record pre-IP administration vital signs.
3. Record patient's body weight pre-IP administration.
4. Ask about and record any AEs since screening (omit if Visit 1 and Visit 2 are combined; see [Section 10.3](#)).
5. IP administration (IV bolus rhPSMA-7.3 [¹⁸F] injection).
6. PET scan as described in the Study Imaging Manual.
7. Record any AEs occurring during the scan process.
8. Perform and record post-IP administration vital signs.
9. Schedule patient for Visit 3 within 7 days post-IP administration.

Optional Visit 2(a): If not already performed, obtain baseline conventional imaging up to 2 weeks following IP administration. Any conventional imaging performed up to 90 days prior to Visit 1 and up to and including Visit 2(a) will be considered baseline conventional imaging.

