4.2 General Presentation Considerations

‘Baseline’ is defined as the last available pre-IP administration assessment, with the exception of baseline imaging which may be performed up to 2 weeks following IP administration if conventional imaging has not been performed within 90 days prior to enrolment.

‘End of Study’ is defined as the last available post-treatment assessment.

‘Study Day’ will be calculated relative to the date of rhPSMA-7.3 (¹⁸F) injection day, and is equal to:

- Assessment Date – IP Administration Date + 1 if the assessment date is on or after IP administration date.
- Assessment Date – IP Administration Date, if the assessment date is before IP administration date.

(i.e. rhPSMA-7.3 IP Administration Date = Study Day 1, the day before IP administration date = Study Day –1))

Continuous data will be summarized in terms of the mean, standard deviation (SD), median, minimum, maximum and number of observations, unless otherwise stated. Continuous data (e.g. counts) that are expected to be skewed will be presented in terms of the maximum, upper quartile, median, lower quartile, minimum and number of observations. The minimum and maximum will be reported to the same number of decimal places as the raw data recorded in the database. The mean, median, lower quartile and upper quartile will be reported to one more decimal place than the raw data recorded in the database. The SD will be reported to two more decimal places than the raw data recorded in the database. In general, the maximum number of decimal places reported shall be four for any summary statistic, irrespective of the previous rules.

Categorical data will be summarized in terms of the number of subjects providing data at the relevant time point (n), frequency counts and percentages. Any planned collapsing of categories will be detailed in the SAP text and the data displays.

Percentages will be presented to one decimal place. Percentages will not be presented for zero counts. Percentages will be calculated using n as the denominator. If sample sizes are small, the data displays will show the percentages, but any textual report will describe frequencies only.

Confidence intervals (CI) will be presented to one more decimal place than the raw data, CI for percentages will be to one decimal place.

Changes from baseline in categorical data will be summarized using shift tables where appropriate.

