4.7 Patient management plans

Patient intended treatment at baseline (before rhPSMA-7.3 (¹⁸F) PET imaging) and post rhPSMA-7.3 (¹⁸F) PET imaging will be listed by subject and time point. The listing will show planned treatments and include details on therapy as applicable, by Subject, Center and Visit. A summary of planned treatment at baseline and post PET imaging (but before confirmatory imaging) by Center and overall will be provided using the FAS.

The options in the intended management plan are:

- Watchful Waiting / Active Surveillance
- Androgen-Deprivation Therapy
- Radiotherapy
- Cryotherapy
- Brachytherapy
- HIFU
- Prostatectomy
- Lymph Node dissection

Parexel International

Blue Earth Diagnostics Ltd
BED-PSMA-302

Statistical Analysis Plan

- Other

The options in the revised management plan are:

- Watchful Waiting / Active Surveillance
- Androgen-Deprivation Therapy
- Radiotherapy
- Cryotherapy
- Brachytherapy
- HIFU
- Prostatectomy
- Targeted treatment of PSMA positive extra-pelvic / bony areas
- Chemotherapy / Immunotherapy
- Lymph Node dissection
- Other

The intended management plan and revised management plan will be compared, and assigned to one of the following categories, for each patient:

- No Change
- Major Change
- Other Change
- Additional Information Required
- Intended Plan Not Valid

The assignment of the category and sub-category in change in management plan to each subject will be performed manually by Blue Earth Diagnostics team, using the SDTM data on the intended and revised management plans provided by Parexel as the source data. An Excel file containing the unique subject ID, category and sub-category in change in management plan.

Patients who have intended management plan but no revised management plan will be considered as having no change in management plan. This is because the question “Is the management plan revised after PSMA scan results available:” is ambiguous – when the site selects “no” as the answer, it is unclear whether this means there is no revision to the management plan, or the management plan after PSMA scan results is not available.

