The use of the phrase “revised management plan” for the management plan after the PSMA scan results can be confusing also, because the management plan is not “revised” as such if it is the same as the intended management plan. Therefore the “intended management plan” and the “revised management plan” will be reworded to “pre-PSMA management plan” and “post-PSMA management plan”, to clearly indicate that the analysis is to compare the management plans before and after PSMA respectively.

The pre-PSMA management plan and post-PSMA management plan will be compared, and assigned to one of the following categories in Table 2, for each patient with both pre-PSMA and post-PSMA plans.

Parexel International

Blue Earth Diagnostics Ltd

BED-PSMA-302

Statistical Analysis Plan

Table 2: Changes in Management Plan

Change in Management Plan Category	Definition
No Change	
When there is no change from the pre-PSMA management plan to the post-PSMA management plan, because:
 
 • The options selected in the pre-PSMA management plan are equivalent to the options selected in the post-PSMA management plan, or • There is a pre-PSMA management plan, and the post-PSMA management plan leading question “Is the management plan revised after PSMA scan results available:” is answered as “no”, or there is no post-PSMA management plan.
Major Change	
When the main options in the pre-PSMA management plan are different from the main options selected in the post-PSMA management plan, and the post-PSMA management plan is clearly a treatment plan.

Minor Change	
When the main options in the pre-PSMA management plan and post-PSMA management plan are the same, but there are some differences in the details (e.g. different radiation fields for radiotherapy)

Additional Information Required	
When the main options in the pre-PSMA management plan are different from the main options selected in the post-PSMA management plan, but the post-PSMA management plan indicates additional diagnostic procedures to be performed (e.g. MRI or biopsy before a decision on treatment plan is taken), or the post-PSMA management plan does not contain clear choice of treatment plan.

Intended Plan Not Valid	
When the pre-PSMA plan does not contain sufficient or clear information on the treatment plan prior to PSMA, or the pre-PSMA plan date is after day 1 (PSMA administration date)

The subcategories in “major change” will be assigned manually using Table 3.

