This analysis considers patients in the EAP who have documented patient management plans in the EDC for before and after the rhPSMA-7.3 (¹⁸F) PET scan. Major and other changes in management plan (see section 4.7) will be summarized showing frequency, proportion (including 95% CI) overall.

4.16.3.6 Reader kappa statistics of rhPSMA7-3 (¹⁸F) scan interpretation by the blinded independent readers.

This analysis considers all patients within the EPSP.

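### Management changes prompted by conventional imaging done between the two plans can be counted as PET effects, because the SAP compares the plans without separating those patients

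*Protocol*

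**What the plan says.** **Pre-scan plan.** Protocol 9.2.4 says that the impact on management "will be assessed by means of both a pre-PSMA PET scan (completed prior to rhPSMA-7.3" imaging) and a post-scan questionnaire. In these, "the investigator will record any changes to the patients' intended management plan based on the" rhPSMA-7.3 PET scan. The protocol therefore asks for changes that follow from PET.

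**Conventional imaging.** Protocol 10.2 provides for Optional Visit 2(a): "If not already performed, obtain baseline conventional imaging up to 2 weeks following IP administration". SAP 4.2 makes the same allowance when it defines baseline: "with the exception of baseline imaging which may be performed up to 2 weeks following IP administration". SAP 4.12.1 counts every conventional scan from 90 days before Visit 1 up to and including Visit 2(a) as baseline conventional imaging.

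**Classification.** SAP 4.7 Table 2 compares the options chosen before and after PET and assigns one of five categories. A pre-scan plan falls under Intended Plan Not Valid if it lacks clear information, "or the pre-PSMA plan date is after day 1 (PSMA administration date"). There is no date rule for the post-scan plan.

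**Confirmatory imaging.** SAP 4.7 places the post-scan plan ahead of confirmatory imaging when it describes "A summary of planned treatment at baseline and post PET imaging (but before confirmatory imaging) by Center and overall", a display on the FAS.

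**Endpoint analysis.** SAP 4.16.3.5 states: "This analysis considers patients in the EAP who have documented patient management plans in the EDC for before and after the" PET scan. It sets no condition on other imaging between the two plans.

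**The concern.** A before-and-after comparison isolates the effect of PET only if PET is the only new information between the two plans. For a patient whose CT, MRI, bone scan or fluciclovine PET is done after the pre-scan plan, there are two new sources of information. If the post-scan plan is completed once both results are known, the comparison cannot tell which one moved the plan, yet the endpoint is worded as a PET effect.

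The date rule in Table 2 raises a separate point. It works on calendar days, so a pre-scan plan written on Day 1 after the scan is accepted. Such a plan may already reflect the PET result, which would hide a real change.

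What is at stake is the meaning of one descriptive secondary percentage. It matters because the study is intended to support PET in the initial workup irrespective of conventional imaging (Protocol section 2), so the change rate should reflect PET alone.

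**Working it through.** The documents give no expected change rate, sample size or power for this endpoint, so there is no figure to reproduce. The check has two parts.

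**1. Order of events**

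| Event | Timing allowed | Source |
|---|---|---|
| Pre-scan plan | Before PET imaging | Protocol 9.2.4 |
| Date check on pre-scan plan | Fails only if dated after Day 1 | SAP 4.7 Table 2 |
| PET | Day 1 | Protocol 10.2 |
| Baseline conventional imaging, if not already done | Visit 1 to 2 weeks after PET | Protocol 9.1.5.1, 10.2; SAP 4.12.1 |
| Discussion of PET results | Visit 3, within 7 days | Protocol 10.4 |
| Confirmatory imaging | Up to 45 days (60 under COVID-19), then up to 90 | Protocol 4.1 |
| Post-scan plan | After PET; ahead of confirmatory imaging in the FAS summary; no date check | Protocol 9.2.4; SAP 4.7 |

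- The questionnaires are not named in the visit lists (Protocol 10.1–10.6) or in the schedules (Protocol Appendix 1, SAP 6.2). Their timing may be set in the eCRF, which is not part of these documents.
- Conventional imaging can fall between the plans in two ways: after PET, or between a pre-scan plan made at Visit 1 and the PET.
- Scans up to Visit 2(a) are baseline by definition, so even a strict rule about confirmatory imaging would not reach them.
- On the combined Visit 1 and Visit 2 pathway, full written consent is taken on Day 1. A pre-scan plan dated Day 1 is then plausible, and its date cannot show whether it preceded the scan.

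**2. Possible size of the overstatement**

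Let
- d = true share of patients whose plan PET changes (assumed 30–50%);
- f = share with conventional imaging after the pre-scan plan and known by the post-scan plan (assumed 10–30%);
- c = chance that this imaging alone would change the plan (assumed 10–30%).

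Patients whose plan PET changes are counted anyway. Only the others can be added wrongly. Treating the two effects as independent:

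reported rate = d + (1 − d) × f × c, so overstatement = (1 − d) × f × c.

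| d | f | c = 10% | c = 20% | c = 30% |
|---|---|---|---|---|
| 30% | 10% | 0.7 | 1.4 | 2.1 |
| 30% | 30% | 2.1 | 4.2 | 6.3 |
| 50% | 10% | 0.5 | 1.0 | 1.5 |
| 50% | 30% | 1.5 | 3.0 | 4.5 |

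Entries are percentage points. Lowest: 0.50 × 0.10 × 0.10 = 0.5. Highest: 0.70 × 0.30 × 0.30 = 6.3. With 316 patients this is about 2 to 20 patients (316 × 0.005 = 1.6; 316 × 0.063 = 19.9).

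For scale, the 95% half-width with 316 patients is 1.96 × √(0.3 × 0.7 / 316) = 5.1 points at a rate of 30% and 1.96 × √(0.25 / 316) = 5.5 points at 50%. The confidence interval does not cover this bias, and the bias does not shrink with more patients.

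**The case against.** There are good arguments on the other side.

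- **The investigator is asked for PET-driven changes.** This is the wording of Protocol 9.2.4, and an investigator may well separate the two sources. It lowers the risk but does not remove it. The eCRF question cited in SAP 4.7 asks whether the plan was revised once PSMA results were available, and the SAP itself calls that question ambiguous. The analysis then compares the two plans and does not use the stated reason.
- **Confirmatory imaging is addressed.** A reader might infer that changes due to confirmatory imaging are counted as PET effects in the same way. The documents do not support that, because SAP 4.7 places the post-scan plan ahead of such imaging. What remains is narrower: the statement belongs to the FAS summary, is not repeated in 4.16.3.5, and has no date check behind it.
- **Not every difference becomes a change.** A reader might also infer that any difference between plans ends as Major or Minor Change. Table 2 sends changed plans that call for further diagnostic work, or lack a clear treatment choice, to Additional Information Required. This removes some plans that are still open, but not one completed after the conventional result is known.
- **The direction is not all one way.** A Day 1 plan written after the scan would lower the rate, as would Table 2's treatment of a missing post-scan plan as No Change wherever it is applied. Nothing shows that pre-scan plans were in fact written after the scan.
- **The effect of conventional imaging may be small.** The protocol describes it as having low sensitivity, which argues for a low c. A post-scan plan completed early would also leave part of the two-week window outside the interval.

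These arguments limit the strength of the point. They do not supply a rule that separates the exposed patients.

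**Conclusion.** The point holds in a limited form. Under the plan as written, a change prompted by conventional imaging done between the two plans can be reported as a PET effect, and neither Table 2 nor SAP 4.16.3.5 identifies the patients concerned. Separately, the Day 1 cut-off in Table 2 is looser than the order required by Protocol 9.2.4, and the two should be reconciled.

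The size is unknown. Under the assumptions above, conventional imaging would add 0.5 to 6.3 percentage points; at the upper end this is similar to the half-width of the confidence interval. None of the three inputs comes from the documents. It would go too far to say that the reported rate will be inflated: only patients with conventional imaging in the interval are exposed to this mechanism, and the other mechanisms act downwards.

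The endpoint is descriptive (Protocol 16.5), and the co-primary tests of CDR and PPV do not depend on it. The change is worth making because it is cheap, but it does not bear on study success.

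**What to change.** 1. **SAP 4.16.3.5.** Keep the result in all EAP patients with both plans as the main figure. Pre-specify a sensitivity analysis, or a separate column, limited to patients whose last baseline conventional scan is dated on or before the pre-scan plan. Where a post-scan plan date is recorded, also require that this plan precede any biopsy, surgery or confirmatory imaging.
2. **SAP 4.7 Table 2.** Align the validity rule with Protocol 9.2.4, so that a pre-scan plan not completed before the PET scan is not valid. Flag Day 1 plans whose order relative to the scan cannot be shown, and report how many there are.

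**Data needed.** Table 2 already uses a pre-scan plan date, and the definition of baseline imaging cannot be applied without scan dates. No section shows that a post-scan plan date is collected, so this should be confirmed before the second condition is written in.

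**Cost.** SAP wording before database lock, a little programming and a smaller denominator in the sensitivity analysis. If 10–30% of 316 patients were set aside for late conventional imaging, about 284 to 221 would remain. The half-width at a rate of 50% would then be 1.96 × √(0.25 / 284) = 5.8 to 1.96 × √(0.25 / 221) = 6.6 points, against 5.5 in all 316. The restriction on the post-scan plan could reduce the number further.

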9.2.5 Adverse Events

AEs will be captured for all patients throughout the study. AEs will be monitored and recorded from the time of informed consent until the last study visit. Duration (start and stop dates and times), severity/grade, outcome, treatment and relationship to IP will be recorded on the eCRF. Patients who experience an SAE or an AE which developed within 3 days of rhPSMA-7.3 (¹⁸F) PET and that persists at the final visit will be followed until resolution or stabilization of these events is recorded.

9.3 Clinical Laboratory Measurements

Not applicable.

10 EVALUATIONS BY VISIT

10.1 Visit 1 (Screening; Day -28 [Within 28 Days Before IP Administration])

1. Review the study with the patient and obtain written informed consent and Health Insurance Portability and Accountability Act (HIPAA) authorization (or equivalent, as required), if appropriate.
2. Assign the patient a unique screening number.
3. Review eligibility criteria and confirm patient suitability for enrollment.
4. Record demographics data.
5. Record medical history and concomitant disease record, including confirmation of a history of localized adenocarcinoma of the prostate with prior curative intent treatment.
6. Record concomitant medications.
7. Perform and record vital signs (omit if Visit 1 and Visit 2 are combined; see [Section 10.3](#)).
8. Commence AE monitoring.
9. Schedule patient for conventional imaging (to take place following Visit 1 and up to 2 weeks after Visit 2) if historical conventional imaging took place greater than 90 days before Visit 1.

Notes:

- a. Conventional imaging that has been performed at non-participating institutions will be accepted provided the scans are reviewed by the participating institution.
- b. Contrast-enhanced CT/MRI and radiopharmaceutical-based baseline conventional imaging (performed as per local standard of care) should be performed at least 24 hours apart from the investigational rhPSMA-7.3 (¹⁸F) PET scan.

10. Schedule patient for Visit 2 within 28 days of consent.

Note: Due to the COVID-19 pandemic, the screening/eligibility evaluation may take place on the day of rhPSMA-7.3 (¹⁸F) administration (with prior pre-screening via telephone) if necessary to ensure the safety of enrolled patients (see Visit 1 and Visit 2 combined; [Section 10.3](#)). Alternatively, the time from Visit 1 (initial screening) to Visit 2 (rhPSMA-7.3 (¹⁸F) PET scan) may be extended up to 45 days due to the COVID-19 pandemic.

10.2 Visit 2 (Day 1; IP Administration)

1. Record any changes in concomitant medication since screening (omit if Visit 1 and Visit 2 are combined; see [Section 10.3](#)).
2. Perform and record pre-IP administration vital signs.
3. Record patient's body weight pre-IP administration.
4. Ask about and record any AEs since screening (omit if Visit 1 and Visit 2 are combined; see [Section 10.3](#)).
5. IP administration (IV bolus rhPSMA-7.3 [¹⁸F] injection).
6. PET scan as described in the Study Imaging Manual.
7. Record any AEs occurring during the scan process.
8. Perform and record post-IP administration vital signs.
9. Schedule patient for Visit 3 within 7 days post-IP administration.

Optional Visit 2(a): If not already performed, obtain baseline conventional imaging up to 2 weeks following IP administration. Any conventional imaging performed up to 90 days prior to Visit 1 and up to and including Visit 2(a) will be considered baseline conventional imaging.

10.3 Visit 1 and Visit 2 Combined (Day 1; IP Administration)

Due to the COVID-19 pandemic, Visit 1 and Visit 2 may be combined (named "Visit 1 and Visit 2 combined") if judged by the investigator to be necessary to decrease potential exposure to SARS-CoV-2 for patients.

If Visit 1 and Visit 2 are combined, please complete all the procedures listed under Visit 1 and Visit 2 ([Sections 10.1](#) and [10.2](#), respectively) after obtaining written informed consent. Omit those procedures identified as not being required if combining visits.

Notes: Visit 1 and Visit 2 combined requires pre-screening via telephone contact prior to Day 1 to review the study eligibility criteria, obtain initial consent (remote consent is acceptable if permitted under local regulations and approvals), to promote study visit compliance and to ensure patient understanding of the combined study visit and planned IP administration, as well as ask about baseline and historic conventional imaging that may already have been performed or needs to be scheduled (note above requirement regarding standard of care baseline conventional imaging).

At sites where IP is not manufactured on-site, IP should be ordered prospectively at least 5 days in advance in accordance with the IP Supply Manual.

For sites with on-site manufacturing, the visits may be combined if mutually agreed by the Radiopharmacy and investigator even post-COVID-19 pandemic restrictions.

Optional Visit 2(a): should still be arranged if required when combining Visit 1 and Visit 2. Any conventional imaging performed up to 90 days prior to screening and up to and including 2 weeks post-combined Visit 1 and Visit 2 will be considered baseline conventional imaging.

